6.3.6 Exposure to treatment

Plasma exchange

The following information will be described at each PE assessment: duration of PE, route used, batch number of albumin, subject weight, product amount, exchange volume, exchange speed.

The number of PE received by visit and during the study will be summarized.

6.3.7 Concomitant medication

All medications will be coded using Anatomical Therapeutic Chemical (ATC) classification codes via the World Health Organization Drug classification Dictionary (WHO-DD), latest version. All medications will be summarized and sorted alphabetically by medication class (i.e., ATC level 2) and medication sub-class (i.e., ATC level 4). If the ATC level 4 term is missing, the ATC level 3 term will be used in the medication summary table and data listing.

Prior medications and concomitant medications will be summarized separately. Prior medications are defined as any medication ended prior to the start of study treatment (i.e., start of PE#1). Concomitant medications are defined as any medication started on or after the start of study treatment or any medication taken prior to the start of study treatment and continued after the start of study treatment during the study.

6.3.8 Adverse events

The Safety Analysis will be based on the safety population.

For summary purposes, adverse events (AEs) will be classified as treatment emergent AEs (TEAEs) or non-treatment emergent AEs (non-TEAEs) depending on the comparison of AE onset date/time with the start of study treatment treatment (i.e., start of PE#1). A TEAE will be defined as an AE which occurred on or after the start of study treatment. Non-TEAEs and TEAEs will be summarized separately.

The number of subjects with any TEAE and the total number of TEAEs will be presented in a summary table, and the characteristics of these adverse events will be described: number of subjects with, and total number of: serious TEAEs, TEAEs leading to death, severe TEAEs, TEAEs related to study drug, TEAEs related to study procedure, TEAEs leading to discontinuation from the study.

In a similar table, the number of subjects with, and the total number of: non-TEAEs, serious non-TEAEs, severe non-TEAEs will be presented.

The proportion of PE sessions temporarily associated with at least one AR (defined as occurring during or within 72 hours after the completion of the product infusion) will be summarized.

The proportion of PE sessions temporarily associated with at least one TEAE, irrespective of causality, during or within 72 hours after the completion of the product infusion, will also be summarized.

The number of subjects with any TEAE will be tabulated and summarized. AEs will be coded in accordance with the Medical Dictionary for Regulatory Activities (MedDRA) AE classification (version 17.0 or higher), and will be tabulated by system organ class (SOC) and preferred term (PT), presented in alphabetic order. This will be done overall, and by severity, causality, and seriousness levels.

Severity (or intensity) of AE:

AEs are classified according to their severity gradation as Mild, Moderate, and Severe.

Causality (relationship) of AE:

AEs will be considered related to the study drug when causality is “definitive”, “probable”, “possible” or “doubtful/unlikely” and such an event will be defined as a suspected AR. A suspected AR with a causal relationship of “definite” will be defined as an AR. On the other hand, when causality is “unrelated”, AEs will be considered as not related to the study drug.

Same rules will apply to define AEs related to study procedure.

In the table presented by causality, 4 classes of causality will be defined:

- related to study drug only
- related to study procedure only
- related to both study drug and study procedure
- not related

Seriousness of AE:

AEs will be distinguished between serious and non-serious AEs, according to the view of either the investigator or Sponsor, depending on its outcome.

Each subject is counted once within each unique SOC and PT level. For example, if a subject has two headaches, the subject is counted only once under the PT “Headache” (worst case in terms of severity, causality, and seriousness will be chosen). Likewise, each subject is counted only once at each SOC level although they may have several different PT events within the same SOC.

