6.1.3. Safety Variables

- Percentage of PE sessions associated with at least one adverse reaction (AR) during or within 72 hours after the completion of the product infusion
- Percentage of PE sessions associated with at least one AE, irrespective of causality, during or within 72 hours after the completion of the product infusion
- Incidence of all AEs
- Vital signs recorded at each assessment visit, before, during, and after each session of PE, and as deemed necessary by the investigator
- Pulse oximetry measurements recorded before, during, and after each PE session
- Clinical laboratory testings (coagulation, blood count, biochemistry, and/or serology) at the specified visit will also be conducted

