11.3. Efficacy Analysis

Efficacy Analysis will be carried out on the evaluable population. The primary efficacy analyses will also be performed using the PP population.

All efficacy variables and changes from the baseline will be summarized by visit.

For the primary efficacy variable, the ALSFRS-R Functional Scale, in addition to the overall score, values of the different functional subdomains will be summarized by visit.

For the co-primary efficacy variable, changes from baseline in the FVC will be summarized by visit.

Changes from baseline in EMG profile, ALS-CBS, ALSA-Q40, and different biomarkers (cytokine panel, neurofilament, BMAA, and immune monitoring profile) will be summarized by visit

In addition, changes from baseline in the levels of cytokine panel, neurofilament levels, and BMAA levels before and after selected PE (PE#7, PE#15, and PE#27) will be summarized and analysed using the non-parametric Wilcoxon test for paired data.

11.4. Safety Analysis.

The Safety Analysis will be based on the safety population.

All AEs (irrespective of causality) will be tabulated and summarized using descriptive statistics.

AEs will be coded in accordance with the AE classification from the MedDRA (version 17.0 or higher), and will be described by a preferred term and the system organ class for severity, causality, and seriousness.

The proportion of subjects and PE procedures temporarily associated with at least one AE/AR will be summarized.

Clinically relevant abnormal changes (according to the investigator's discretion) in vital signs and any other laboratory parameter shall be recorded as AEs. The same will be done with relevant abnormal changes in any such parameter during the follow-up period.

Clinical laboratory parameters and changes from baseline values will be summarized by visit. Vital signs and changes from baseline values will be summarized by visit.

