- Table 14.3.1.2 Summary of TEAEs – Safety Population
- Table 14.3.1.3 PE sessions temporarily associated with AR, occurring during or within 72 hours after the completion of the product infusion – Safety Population
- Table 14.3.1.4 PE sessions associated with TEAE, occurring during or within 72 hours after the completion of the product infusion – Safety Population
- Table 14.3.1.5 TEAEs: MedDRA coding by SOC and PT – Safety Population
- Table 14.3.1.6 TEAEs: MedDRA coding by severity, SOC and PT – Safety Population
- Table 14.3.1.7 TEAEs: MedDRA coding by causality, SOC and PT – Safety Population
- Table 14.3.1.8 TEAEs: MedDRA coding by seriousness, SOC and PT – Safety Population

List of deaths and other serious adverse events

- Table 14.3.2.1 Adverse events leading to death – Enrolled Population
- Table 14.3.2.2 Adverse events leading to discontinuation from the study – Enrolled Population
- Table 14.3.2.3 Serious adverse events – Enrolled Population

Laboratory data

- Table 14.3.3.1 Complete Blood Count: absolute values and change from baseline by visit – Safety Population
- Table 14.3.3.2 Complete Blood Count: summary of shift of values by visit – Safety Population
- Table 14.3.3.3 Biochemistry and Lipid Profile: absolute values and change from baseline by visit – Safety Population
- Table 14.3.3.4 Biochemistry and Lipid Profile: summary of shift of values by visit – Safety Population
- Table 14.3.3.5 Serum Electrolytes: absolute values and change from baseline by visit – Safety Population
- Table 14.3.3.6 Serum Electrolytes: summary of shift of values by visit – Safety Population
- Table 14.3.3.7 Coagulation: absolute values and change from baseline by visit – Safety Population
- Table 14.3.3.8 Coagulation: summary of shift of values by visit – Safety Population
- Table 14.3.3.9 Fibrinogen: absolute values and change from baseline by visit – Safety Population
- Table 14.3.3.10 Fibrinogen: summary of shift of values by visit – Safety Population
- Table 14.3.3.11 Serology results by visit – Safety Population

Concomitant therapy

Table 14.3.4.1 Prior medication – Safety Population
Table 14.3.4.2 Concomitant medication – Safety Population

Other safety data

Table 14.3.5.1 Vital signs during evaluation visits: absolute and change from baseline values by visit – Safety Population
Table 14.3.5.2 Vital signs during PE: change from pre-PE assessments – Safety Population

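### The SAP reports events within 72 hours of an exchange per session only, leaving out the per-subject proportion that the protocol also commits to

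*SAP*

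**What the plan says.** Protocol 11.4 (Safety Analysis) states: "The proportion of subjects and PE procedures temporarily associated with at least one AE/AR will be summarized". The synopsis makes the same commitment. Both name two units of analysis, the subject and the procedure.

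SAP 6.3.8 carries over only the second. For reactions it plans "The proportion of PE sessions temporarily associated with at least one AR", and for events of any cause "The proportion of PE sessions temporarily associated with at least one TEAE, irrespective of causality". The table shells match. Table 14.3.1.3 covers "PE sessions temporarily associated with AR, occurring during or within 72 hours after the completion of the product infusion", and the other is "Table 14.3.1.4 PE sessions associated with TEAE, occurring during or within 72 hours after the completion of the product infusion".

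The protocol's list of safety variables (6.1.3) is itself per session: "Percentage of PE sessions associated with at least one adverse reaction (AR) during or within 72 hours after the completion of the product infusion", with a parallel item for AEs. SAP 4.3 reproduces that list. The subject-level commitment therefore sits in the protocol's analysis text (11.4 and synopsis), not in its variable list.

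The SAP does count subjects in other ways. The TEAE summary in 6.3.8 gives the "number of subjects with, and total number of: serious TEAEs, TEAEs leading to death, severe TEAEs, TEAEs related to study drug", followed by procedure-related TEAEs and TEAEs leading to discontinuation. There are also tables by system organ class and preferred term, severity, causality and seriousness.

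**The concern.** The safety objective is the tolerability of the exchange procedure. In a pilot of about ten people, a basic tolerability result is how many of them had an event during or shortly after an exchange. The protocol planned to report that. Someone programming from the SAP would not produce it, and the SAP gives no reason for the change.

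The retained measure cannot stand in for it. Each subject may contribute up to 27 sessions, so the session percentage answers a different question (how often a session is affected) and gives most weight to whoever receives most sessions. Protocol 6.2.3 foresees fewer than 27 sessions when laboratory changes, clinical factors or AEs prevent an exchange. Protocol 4.4 allows withdrawal because of an AE. Sessions received can therefore depend on tolerability.

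**Working it through.** **1. Inputs**
- Sessions per subject: 2 per week × 3 weeks + 1 per week × 21 weeks = 6 + 21 = 27, which reproduces the protocol's figure (synopsis, 5.1).
- Subjects: 10 completing treatment (protocol 4.3), so 10 × 27 = 270 sessions.
- Window: during or within 72 hours after completion of the infusion (protocol 6.1.3, SAP 6.3.8). I read the documents' word for association as *temporally*.
- Event and withdrawal rates: none are given. The patterns below are assumptions chosen to show what the measure can and cannot distinguish.

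**2. Does the session percentage identify the number of subjects?**

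Session percentage = affected sessions / all sessions. Take 27 affected sessions: 27/270 = 10%.
- One subject affected at all 27 sessions: 1/10 = 10% of subjects.
- All ten affected, seven of them three times and three twice (7 × 3 + 3 × 2 = 27): 10/10 = 100% of subjects.

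The same 10% of sessions is compatible with anything from 10% to 100% of subjects.

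**3. What happens when affected subjects leave early?**

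This applies to the TEAE table only. Protocol 7.1.3.3 requires reappearance on rechallenge for *definite* causality, and only definite events are ARs, so a subject with one event who then leaves would not normally count as an AR. Suppose 2 of 10 subjects have a TEAE at PE#1 and the other eight complete with none.

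| Pattern for the two subjects | Affected / all sessions | Sessions | Subjects |
|---|---|---|---|
| Leave after PE#1 | 2 / (8 × 27 + 2) = 2/218 | 0.92% | 20% |
| Stay, no further event | 2/270 | 0.74% | 20% |
| Stay, affected every time | 54/270 | 20.0% | 20% |

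Compared with staying, leaving raises the session figure slightly if the event would not have recurred, and lowers it sharply if it would have recurred every time. With three such subjects the pattern is the same: 3/192 = 1.6% if they leave, against 3/270 = 1.1% or 81/270 = 30.0% if they stay. The direction depends on an unknown, while the subject proportion does not move. The exact 95% interval for 2/10 is 2.5% to 55.6%, so the subject proportion is imprecise, but it does answer the question.

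**4. Do the SAP's other subject counts fill the gap?**
- *Time.* TEAEs run from PE#1 to the final visit (protocol 7.1.3.3, SAP 6.3.8). That includes the follow-up from the last exchange at week 24 to week 48. No tabulated subject count is limited to 72 hours.
- *Causality.* In SAP 6.3.8, related means definite, probable, possible or doubtful/unlikely, whereas an AR is definite only. The causality table does not separate these: "In the table presented by causality, 4 classes of causality will be defined", namely drug only, procedure only, both, and not related.

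No SAP table therefore gives the number of subjects with a TEAE in the window, or with an AR.

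**The case against.** The strongest case for the SAP is that little is lost. Protocol 6.1.3 defines the windowed variables per session, and SAP 4.3 follows it faithfully. Subjects who stop because of an event appear in the count of TEAEs leading to discontinuation and in Table 14.3.2.2. Table 14.3.5.5 shows how many exchanges were received. The AE and exchange listings (16.2.6.1 and 16.2.10.1) would let a reader count affected subjects by hand. The study is descriptive and uncontrolled, and the missing count changes no test or decision rule.

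Most of that stands, and it limits the size of the point. SAP 4.3 is not a departure from the protocol and needs no correction. Subject-level evidence of intolerance is not absent from the SAP. But a count that can be reconstructed from listings is not the summary that protocol 11.4 says will be produced, and none of the tabulated counts is equivalent to it.

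A reader might also infer that early leavers always dilute the session percentage, so that it systematically understates risk. The documents do not support that. As the table above shows, leaving lowers the figure only if those subjects would have gone on being affected, and otherwise it can raise it. Nor would a subject row for ARs reliably expose people who had one event and left, because the protocol's definition of a definite reaction requires rechallenge. For them the TEAE row is the informative one.

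**Conclusion.** The mismatch is real and can be confirmed by reading: the protocol commits to two proportions and the SAP delivers one, without explanation. Its practical meaning is that the session percentage alone cannot say how many subjects are affected. On the planned 270 sessions, a 10% session rate fits any share of subjects from 10% to 100%.

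This rests on ten subjects with 27 sessions each; the event patterns are illustrative, since the documents give no rates. It also assumes that the association in protocol 11.4 refers to the 72-hour window, as SAP 6.3.8 and protocol 6.1.3 use it.

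This should be corrected, because it drops a planned result on the stated safety objective. It does not undermine the safety analysis as a whole.

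**What to change.** In SAP 6.3.8 and in Tables 14.3.1.3 and 14.3.1.4, add the number and percentage of safety-population subjects with at least one AR, and with at least one TEAE, during or within 72 hours after an exchange. Show these beside the session percentages. Listing each subject's affected and received sessions would help but is optional, since the protocol does not promise it. If the sponsor prefers to keep sessions only, the SAP should state the departure from protocol 11.4 and the reason.

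The cost is a few extra table rows. AE onset date and time are already on the CRF (protocol 7.1.3.7) and exchanges received are already summarised (SAP 6.3.6), so no new data are needed.

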7.1.2. Adverse Event Monitoring

Subjects must be carefully monitored for AEs. This monitoring includes clinical and laboratory tests and physical signs. AEs should be assessed in terms of their seriousness, severity, and causal relationship to the investigational product.

The investigator is responsible for the detection and documentation of events that comply with the criterion and definition of an AE or a serious adverse event (SAE), in accordance with that set forth in this protocol. AEs and SAEs will be documented from the time the subject signs the informed consent before the first PE and until the subject returns for the last study visit, whether the subject has completed the study or has stopped prematurely for any reason.

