7.1.3.3. Causality of Adverse Event

The Investigator is required to provide a causality assessment for each AE reported to the Sponsor. The Sponsor will consider the Investigator’s causality assessment. Assessment of the causal relationship to the study drug will be made according to the following classifications based on Karch FE, et al.(67)

- **Definite:** an event that follows a reasonable temporal sequence from administration of the treatment or in which the treatment level has been established in body fluids or tissues; that follows a known response pattern to the suspected treatment; and that is confirmed by improvement on stopping the treatment (dechallenge), and reappearance of the event on repeated exposure (rechallenge).
- **Probable:** an event that follows a reasonable temporal sequence from administration of the treatment; that follows a known response pattern to the suspected treatment; that is confirmed by dechallenge; and that could not be reasonably explained by the known characteristics of the subject's clinical state.
- **Possible:** an event that follows a reasonable temporal sequence from administration of the treatment that follows a known response pattern to the suspected treatment but that could have been produced by the subject's clinical state or other modes of therapy administered to the patient.
- **Doubtful/Unlikely:** an event that follows a reasonable temporal sequence from administration of the treatment; that does not follow a known response pattern to the suspected treatment; but that could not be reasonably explained by the known characteristics of the subject's clinical state.
- **Unrelated:** any event that does not meet the criteria above.

The operational tool to decide the AE causal relationship is based on algorithms by Karch et al. and Naranjo et al.(68,69) When an AE is classified, assessing causal relationship by the Investigator, as "definite", "probable," "possible" or "doubtful/unlikely," the event will be defined as a suspected AR. A suspected AR with a causal relationship of "definite" will be defined as an AR. When the causal relationship is labeled "unrelated," then it will be considered that the AE is not imputable to the study treatment and it is not a suspected AR.

In addition, when a causal relationship between the study treatment and the AE cannot be ruled out by the Investigator and/or Sponsor, it means that the AE cannot be labeled "unrelated."

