7.1.3.7 Adverse Event Documentation

All AEs and SAEs occurring from the subject’s **signing of the informed consent form (ICF)** until last day of subject’s participation in clinical trial must be fully recorded in the subject’s CRF or/and SAE form, respectively. If no AE has occurred during the study period, this should also be indicated in the CRF.

It is responsibility of the Investigator to ensure that AEs are appropriately recorded.

At each visit, AEs will be elicited by asking the individual a non-leading question such as “Do you feel different in way since the last visit?” Moreover, AEs will also be collected through directly observed events or spontaneously volunteered by the subject. Clearly related signs, symptoms, and abnormal diagnostic procedures should preferably be grouped together and recorded as a single diagnosis or syndrome wherever possible.

The following variables must be recorded on the AE CRF entry:

1. The verbatim term (a diagnosis is preferred)
2. Date/time of onset
3. Date/time of resolution
4. Severity (mild, moderate, severe)
5. Causality (unrelated, doubtful/unlikely, possible, probable, definite)*
6. Seriousness (yes, no)
7. Action taken (with regard to investigational product)
8. Other action (to treat the event)
9. Outcome and sequel (follow-up on AE)

**Causality assessment will be only made when the AE occurs after the subject has received the study treatment. AE occurring before subject’s exposure to investigational product will be always labeled as “unrelated.”*

In addition to the Investigator’s own description of the AEs, each AE will be encoded by the Sponsor according to the Medical Dictionary for Regulatory Activities (MedDRA®).

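### SAP 6.3.8 needs a drug grade and a procedure grade for every adverse event, but the protocol specifies one grade only, to the investigational product

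*SAP*

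**What the plan says.** **SAP.** Section 6.3.8 treats an AE as drug-related when its grade is anything other than unrelated, and adds: "Same rules will apply to define AEs related to study procedure". The TEAE summary is to count "TEAEs related to study drug, TEAEs related to study procedure, TEAEs leading to discontinuation from the study". The table by causality (Table 14.3.1.7) has four classes, two of which are "related to study procedure only" and "related to both study drug and study procedure". No variable or derivation is named for procedure causality, and study procedure is not defined.

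**Protocol.** Section 7.1.2 states: "AEs should be assessed in terms of their seriousness, severity, and causal relationship to the investigational product". Section 7.1.3.3 introduces the five-grade scale with "Assessment of the causal relationship to the study drug will be made according to the following classifications". Among the nine items that 7.1.3.7 requires on the AE CRF entry, the fifth is "Causality (unrelated, doubtful/unlikely, possible, probable, definite"), and there is no second causality item. Section 7.1.3.8 likewise asks that AEs arising from laboratory abnormalities be described by their relationship to the investigational product.

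**The concern.** The safety objective (Protocol 2.3, SAP 2.3) is about how safe and tolerable the procedure is. Protocol 7.1.1 lists the events expected from plasma exchange (PE), such as hypocalcemia, coagulation disorders and hypotension, apart from the reactions to albumin. The protocol therefore sees two sources of harm, and the SAP promises to report them separately, but no input for the second source is specified.

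If the field is missing, someone has to decide at programming or reporting which events the procedure caused, in open-label data and without a stated rule. The stopping rules in Protocol 4.4 rest on the same distinction: they count product-related SAEs and leave out those put down to the procedure or technique. The investigator and sponsor must make that judgement, but no scale or listed item supports it.

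**Working it through.** No arithmetic in the plan bears on this point, so the check compares what the SAP needs with what the protocol specifies.

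| Place | Object of the causality judgement | Grades per AE |
|---|---|---|
| SAP 6.3.8, TEAE summary and Table 14.3.1.7 | study drug and, separately, study procedure | 2 |
| Protocol 7.1.2 | investigational product | 1 |
| Protocol 7.1.3.3 | study drug, five grades | 1 |
| Protocol 7.1.3.7, AE CRF items | one causality item (5 of 9), object not named | 1 |
| Protocol 7.1.3.8, laboratory AEs | investigational product | 1 |

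**Can the four classes be derived?** Two yes/no results give 2 × 2 = 4 classes. One yes/no result gives 2. A yes for the drug pools drug only with both; a no pools procedure only with not related. In practice a programmer could fill drug only and not related, and would leave the other two classes and the procedure-related row empty.

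**Where would an event caused by PE go?** The text allows two routes.

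1. *To not related.* The investigator grades strictly against albumin. Hypocalcemia during an exchange, which 7.1.1 attributes to PE, is then graded unrelated to the product, and the SAP has nothing else to count it under.
2. *To drug only.* Section 7.1.3.2 defines suspected reactions against a medicinal product or study treatment, and the synopsis describes treatment as 27 PEs with Albutein 5%. Under 7.1.3.3 the doubtful/unlikely grade counts as related. It covers an event in plausible time sequence that lacks the treatment's known pattern and is not explained by the patient's condition. The unrelated grade is also barred when a link to study treatment cannot be excluded. Read this way, the same hypocalcemia is related and is reported as drug only.

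Which route applies depends on how the investigator reads study treatment.

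**Exposure.** If 10 subjects complete treatment, there are 27 × 10 = 270 exchanges. Two of the three lumbar punctures per subject (week 12 and week 25, Protocol 6.2.5 and 6.2.7) fall after the first PE, so 2 × 10 = 20 punctures could give rise to TEAEs. The SAP does not say whether these punctures count as study procedure.

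**Two knock-on gaps in SAP 6.3.8.** The worst-case rule for repeated events within a preferred term gives no order between drug only and procedure only. It is also unclear whether an event definitely caused by the procedure becomes an adverse reaction (AR), which matters for the percentage of PE sessions with an AR.

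**The case against.** The strongest reply is that the CRF is not among the documents. Section 7.1.3.7 lists what must be recorded, which is a minimum. The SAP, dated April 2019, describes other data that the protocol does not list: sensory nerve conduction, CSF IgG and a leucocyte differential. It may therefore have been written from a CRF that already holds a procedure field, and its phrase about the same rules fits that. The protocol also expects procedure attribution elsewhere (4.4, 7.1.3.5, 7.1.4.1). This stands, so a reader who infers that no source data exist goes too far. The documents show only that the protocol does not specify the data and the SAP does not name them.

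A reader might also infer that PE harm will disappear into the not-related class. The second route above shows that the text equally allows it to inflate drug-related counts.

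A third tempting inference starts from 7.1.3.7: "Causality assessment will be only made when the AE occurs after the subject has received the study treatment". Earlier events are labelled unrelated, so complications of the baseline lumbar puncture might seem to be lost. They are non-TEAEs, however. Their planned summary has no causality row, and Table 14.3.1.7 covers TEAEs only, so no planned causality output changes.

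Finally, PE events stay visible whatever their grade: PE sessions with any TEAE up to 72 hours after infusion (Table 14.3.1.4), all TEAEs by system organ class and preferred term (14.3.1.5) and SAEs (14.3.2.3). That also stands. It limits the damage to the causality outputs but does not supply their missing input.

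**Conclusion.** The point holds as a mismatch between the protocol and the SAP. The SAP needs two causality grades per AE and the protocol specifies one. If the data were collected only as the protocol lists them, two of the four causality classes and the procedure-related TEAE row cannot be produced, and the other two classes may be wrong in either direction. The number of events that would change class cannot be estimated before data. The all-cause AE tables and the efficacy analyses are unaffected.

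The conclusion about derivability assumes that the CRF has no second causality field. If it has one, what remains is a traceability gap: the variable is unnamed and study procedure is undefined. In either case it should be corrected, because this is a planned output for an objective about the procedure and the correction is cheap.

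**What to change.** - **Protocol.** Add causality to study procedure to the required AE items in 7.1.3.7, on the same five grades and judged by the investigator, and align 7.1.2.
- **SAP 6.3.8.** Name the procedure-causality variable. Define study procedure: PE and vascular access, and whether the week 12 and week 25 lumbar punctures count. In the same paragraph, state the class order for the worst-case rule and whether a definite procedure grade makes an AR.
- **If the field was not collected.** Either have the investigator grade existing TEAEs in one documented query round before database lock, with those grades flagged as retrospective, or drop the four-class split and the procedure-related row.

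The cost is one CRF item, a few sentences and at most one query round. If the CRF already has the field, only the wording changes. The drawback is that events already recorded would be graded in retrospect, in open-label data. The flag keeps that visible; dropping the split avoids it but loses the separate report on the procedure.
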